5.0 Study Procedures

The intervention period will last 3 months. The baseline outcome assessment will be conducted in person or virtually (via Microsoft Teams or over the phone) and in a private space. All other outcomes will be completed in person, virtually, or mailed. If the interview is completed in person or on the phone it will occur in a private space. *Upon approval of the June 27, 2022 (A033) amendment, the study team will no longer complete 6-month interviews for participants who enroll after this date.* The length of follow-up and schedule of outcome assessments at 1, 3, and 6 months (6-months pre A033 only) (see table 2 below) are to detect three types of treatment effects: 1) "early response" (at 1 month); 2) immediate post-intervention benefits at 3 months; and 3) sustained effects at 6 months post-randomization (3 months post-intervention). Study subjects (Veterans) will be reimbursed \$25 per completed outcome assessment (with 4 scheduled assessments each (baseline, 1, 3, and 6 months). Completion/payment of 6-month interviews will be for those enrolled prior to A033 approval only.

Table 2: Outcome Assessment Protocol: Measures and Schedule of Administration

Domain	Measure	Items	Time (min)	Schedule			
				BL	1 mo	3 mo	6 mo
Covariates	Demographics; disability compensation, comorbidity;	36	10	X			

	range of motion, treatments, BMI, medication list						
Neck pain disability	Neck Disability Index	10	3	X	X	X	X
Pain Severity	Brief Pain Inventory	10	3	X	X	X	X
Pain Interference	PROMIS—pain	4	1	X	X	X	X
Psychological	PHQ-9 Depression	9	2	X		X	X
	PROMIS-Depression	9	2	X		X	X
	GAD-7 Anxiety	7	2	X		X	X
	VA PTSD Screener	4	1	X		X	
	PTSD-PCL-17 (if screen positive)	17	5	X		X	
	Stress	10	3	X		X	
Generic HRQL	Medical Outcomes Study VR-36	36	10	X	X	X	X
Sleep	MOS Sleep Scale	12	3	X		X	
Somatic	Somatic Symptom Scale-8	8	3	X		X	X
	SSD-12	12	4	X		X	X
Pain beliefs	Pain Catastrophizing Scale	13	3	X		X	
Social support	Social Support Scale	12	2	X		X	
Treatment satisfaction	Pain-specific satisfaction	3	2		X	X	X
Intervention credibility	EXPECT Questionnaire	4	2	X		X	
Perceived Response	Global Impression of Change	1	1	X	X	X	X

Therapist-treated massage

Participants randomized to the therapist-treated massage (TT-M) arm will receive a standardized Swedish massage protocol tailored to chronic neck pain as used in [name] studies. We chose a Swedish massage protocol because they are the most widely taught and

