New modification sample size: For the comparison of the TT-M and the waitlist control group (WL-C) we need 100 patients per group ($N = 200$) by 3 months to have 80% power to detect a 0.4 SD difference in change in NDI from baseline between TT-M and control with Type I error = 0.05 for the comparison of interest: TT-M vs WL-C. All analysis will be conducted under the intention-to-treat principle. Sample size was derived based on an independent two-sample t-test which is conservative compared to the contrast from our proposed linear mixed model.

Previously we assumed a total attrition for the TTM and WL-C arm of $(27+20)/(98+99) = 47/197 = 24\%$, thus we sought to enroll a Total $N = 264$ ($200/.76$) or 132 per group in the TT-M and WL-C study groups. We will now enroll Total $N = 296$ ($264 + 16 \times 2$) so that we will

have an additional 16 in the TTM arm to account for the 16 that were paused due to COVID but will also maintain the current randomization allocation. For IRB purposes, we will continue to recruit to reach at most N = 308 this would increase the 16 COVID paused to also account for potential 24% attrition (16/.76 = 22 per group). However, this is not necessarily required as the COVID paused will still be included in the linear mixed model up until their one month assessment. This should allow us to reach our sample size of 100 per group to complete the 3 month assessment.

Data analysis: Baseline characteristics of TOMCATT sample

As an RCT, we expect characteristics of study participants to be balanced across the two study arms. We will compare all baseline demographic and clinical characteristics between the treatment groups using the appropriate test (ie, ANOVA, Kruskal-Wallis test, or Chi-square test). Variables found to significantly differ will be included in subsequent regression models.

Main analysis (Aim 1) of the primary outcome (NDI total score)

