All outcomes will be collected at baseline, 1, 3, and 6 months. Six-month outcomes will only be collected for those who consent prior to approval of A033. For the primary outcome of Neck Disability Index (NDI) total score, we will use a linear mixed effect model with an appropriate covariance structure to compare the treatment arm to the control arm on rate of change as well as difference in outcome at the 3-month time point. Fixed effects will include treatment, time (as categorical), and treatment by time interaction. Difference in amount of change in outcome between groups at the other time points (1 and 6 months (pre A033 only)) will also be estimated and reported. We will examine the associations among the repeated measures within subjects and use a data driven approach in determining the appropriate variance-covariance structure.⁷¹ We will use the Šídák method to adjust for multiple comparisons. All analyses will include checking of assumptions and model fit. We plan intent-to-treat with the primary endpoint at 3 months and evaluation of "early" response at 1 month and "sustained" response at 6 months post-randomization (pre A033 only).

Analysis of secondary outcomes (Aim 2)

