Since this study is not specifically powered for secondary outcomes, these results should be interpreted cautiously. Pain intensity, pain interference, health-related quality of life (HRQL), depression, anxiety, and pain cognitions are all continuous measures. These subscales will be analyzed with the same approach as the primary outcome. For the pain intensity score, we will also report a clinically relevant descriptive statistic in which we define patients with > 30% reduction from baseline as "responders." For the NDI, a "responder" will be defined as a decrease of more than 5 points from baseline. This binary outcome will be observed at 1, 3, and 6 months (pre A033 only) for each participant. A generalized linear mixed model with predictors of group, time, and their interaction will be used that also includes a random subject effect to accommodate the potential correlation among observations from the same participant. The primary contrasts of interest will be the difference in proportions at 3 months between each treatment and the control group. We will use the Šídák method to adjust for multiple comparisons. Differences in proportions between treatment groups at the other time points will also be reported. For exploratory measures regression models will be used based on data type and will include pain coping, sleep problems, satisfaction, and social support.

Moderator analyses

As a secondary analysis for the primary outcome (NDI) as well as secondary outcomes, we will test baseline anxiety (GAD-7 and PTSD) and depression (PHQ-9) as moderators. This will be done separately for each potential moderator by re-running each mixed model for primary and secondary outcomes while additionally including the moderator, the moderator by treatment group interaction, and the moderator by treatment by time interaction. The treatment by time by moderator interaction represents the moderation effect on the treatment difference. If the treatment term is significant then moderation is occurring. Testing these measures as moderators will provide insight into generalizability of the interventions. For example, if the intervention loses effect in patients with high anxiety or depression, these patients may not be suited to the intervention.

Missing data

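### Covariates are chosen by baseline significance tests, and neither sex nor a shared NDI baseline is prespecified; naming them in advance is a free improvement, not a repair of an invalid primary test

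*Combined protocol and SAP*

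**What the plan says.** - **Covariate rule** (section 8.0, Baseline characteristics of TOMCATT sample): "We will compare all baseline demographic and clinical characteristics between the treatment groups", followed by "Variables found to significantly differ will be included in subsequent regression models". No test level is given, and nothing says whether a selected variable enters as a main effect or also by time.
- **What is available to test** (section 5.0, Table 2): 17 scales are marked at baseline, plus a covariate row covering seven kinds of variable, including "range of motion, treatments, BMI, medication list".
- **Randomisation** (section 4.0): stratified by sex, in blocks of 4 within strata. Sex appears in no model.
- **Primary NDI model** (section 8.0, Main analysis): "Fixed effects will include treatment, time (as categorical), and treatment by time interaction". The section names both the rate of change and the outcome difference at 3 months. For the other visits it refers to "Difference in amount of change in outcome between groups at the other time points".
- **Responder analysis** (section 8.0, Aim 2): "A generalized linear mixed model with predictors of group, time, and their interaction will be used", with a random subject effect. "The primary contrasts of interest will be the difference in proportions at 3 months". No baseline score is listed.
- **Exploratory measures** (same section): "For exploratory measures regression models will be used based on data type". No covariates are named.
- **Co-interventions** (section 5.0): adjustment for differences in care between arms is also mentioned, without saying in which analysis.

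**The concern.** A significant baseline difference in a properly randomised trial is a chance event. Choosing covariates that way selects on imbalance rather than on prognosis, and the final model is unknown until the arms have been compared. The one variable the design singles out, sex, is balanced by the blocking, so the rule is very unlikely to choose it.

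The primary model raises a separate efficiency question. All randomised patients are to be analysed, and paused patients stay in the model up to their 1-month visit. Baseline NDI is therefore most naturally read as one level of the response, with its own mean in each arm. That is valid, but it ignores the fact that randomisation makes the two baseline means equal in expectation.

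At stake are the reproducibility of the secondary results, an unambiguous primary contrast, and precision from data already collected.

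**Working it through.** **1. The plan's own figure.** Two-sample t-test, difference 0.4 SD of change, two-sided 0.05, 100 per arm: power 80.4%. The stated 80% reproduces. So do 200/0.76, about 264, and 264 + 32 = 296.

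**2. How often the rule fires** (level 0.05 assumed). Expected chance picks are 0.05 × 17 = 0.85, or 0.05 × 24 = 1.2 with the seven covariate kinds added. The chance of at least one pick, if the variables are independent, is 1 − 0.95^17 = 58% or 1 − 0.95^24 = 71%. At a correlation of 0.5 between variables it is 39% or 46%.

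**3. Sex.** With 1:1 blocks of 4, the largest imbalance within a stratum is 2. Take 296 patients, 20 of them women split 11 to 9, and the men split 137 to 139. The chi-square p-value is 0.64, and it is larger with more women (up to 148). The block layout while a third arm existed is not documented, but under any valid randomisation the chance of picking sex is at most about 5%. If sex explained 1-5% of the variance of change (assumed), omitting it makes the SE too large by 1/√0.99 = 1.005 to 1/√0.95 = 1.026.

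**4. Effect of picks on the NDI contrasts.**
- *Change to 3 months, main-effect picks.* A term that is constant over visits cancels from the within-patient difference, so with complete data the shift is zero. In simulation with 132 per arm, 24% dropout and a picked covariate with a 0.3-SD effect, the mean shift was 0.04-0.05 SE and the largest 0.17 SE.
- *Level difference at 3 months.* In simulation under no effect with 17 correlated baseline variables, selection moved the estimate by up to about 0.5 SD. Type I error fell to 2.2-3.1%, so the test became conservative.
- *Picks entered by time.* The cancellation no longer holds, and the change contrast becomes data-dependent too.

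**5. Responder model.** A 3-month logistic regression stood in for the mixed model. Assumptions: 100 per arm, baseline SD 7, mean control change −2, effect 0.4 SD of change. When baseline NDI reaches p < 0.05 (about 5% of trials), the log odds ratio moves on average 0.2-1.1 SE. Averaged over all trials the shift is 0.01-0.06 SE, and significance changes in about 0.5-2% of trials. Always including baseline NDI changes power by −1 to +9 points (for example 61% to 70% at k = 1, ρ = 0.4). Type I error stays near 5% either way.

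**6. Shared baseline mean.** Let ρ be the correlation of baseline with 3-month NDI, and k the 3-month SD divided by the baseline SD. Neither is in the documents; the ranges used are assumptions. With complete data:

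variance ratio (shared / free) = k²(1 − ρ²) / (1 + k² − 2ρk)

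Example, k = 1 and ρ = 0.5: 0.75 / 1 = 0.75. The standardised effect becomes 0.4/√0.75 = 0.46, and power is 90.1%. Power with 100 per arm, against 80.4% with free baselines:

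| k | ρ = 0.4 | 0.5 | 0.6 | 0.7 |
|---|---|---|---|---|
| 1.0 | 92.0% | 90.1% | 88.2% | 86.3% |
| 1.2 | 87.6% | 85.5% | 83.4% | 81.7% |
| 1.3 | 85.9% | 83.8% | 82.0% | 80.7% |

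**7. At the current enrolment.** There are 148 per arm, with the 16 paused patients lost in TT-M only. Completers are 0.76 × (148 − 16), about 100, in TT-M and 0.76 × 148, about 112, in the control arm. Losses in each arm are split evenly between after baseline and after month 1. Three-visit generalised least squares was used with known covariance, 1-month SD (1 + k)/2 and 1-month correlations ρ + 0.1. Free baselines give 84.7-86.6% power and a shared baseline 85.1-94.0%, a gain of about 0.2 to 7 points.

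**The case against.** The best defence is that nothing here is broken. The change contrast is unbiased, holds its size and meets its power target; at 148 per arm it exceeds it. The shared baseline is an efficiency choice whose gain depends on quantities the documents do not give. Sex contributes almost nothing, and leaving it out errs on the conservative side. The responder analysis is secondary, the plan itself asks for caution there, and when the rule picks baseline NDI it makes the adjustment recommended here. All of that stands, and it limits the point to an improvement.

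It does not rescue the rule. The plan names the 3-month level difference alongside the change, and selection does move that contrast. The plan also does not restrict picks to main effects, so the protection of the change contrast rests on a reading it never states. Neither the covariate row of Table 2, which lists data to collect, nor the co-intervention adjustment, which concerns care during the study, is a prespecified baseline adjustment set.

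A reader might infer that testing for imbalance inflates type I error, biases the primary result or leaves the trial underpowered. The calculations show none of these. A reader might also take the shift of up to 1.1 SE as typical for the responder result; it applies only in the roughly 5% of trials where baseline NDI is picked.

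**Conclusion.** The point holds as a free improvement. The covariate rule selects on chance and leaves the level difference, the responder model and the exploratory models dependent on baseline p-values; the change contrast joins them if picks enter by time. The usual effect on the responder estimate is small, and occasionally it is material.

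The unused precision comes almost entirely from baseline NDI, not sex. It ranges from near zero to about 12 points of power with 100 complete per arm (80.4% to 92.0%), and is never negative for ρ 0.4-0.7 and k 1.0-1.3.

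This rests on those assumed ranges, a 0.05 selection level, the single-visit stand-in for the responder model, and the inference that baseline NDI is a response level. It does not threaten the primary conclusion.

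**What to change.** Before any comparison between arms:

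- **Baseline section:** delete the sentence that admits variables by significance, and report baseline data descriptively.
- **Primary model:** state that the response is NDI at baseline, 1, 3 and (where collected) 6 months. Fixed effects are time, treatment by post-baseline time with one baseline mean shared by the arms, sex, and sex by time. The single primary contrast is the treatment difference at 3 months. This keeps patients who have only a baseline score and makes the change contrast and the 3-month difference the same quantity. Sex by time is needed because a sex effect constant over visits cancels from the change.
- **Continuous secondary outcomes:** use the same form.
- **Responder models:** include sex and the baseline score of the outcome whatever the baseline comparison shows. Obtain the difference in proportions by averaging predictions over patients with the random subject effect integrated out.
- **Exploratory regressions:** name sex and, where measured, the baseline value in advance.
- **Co-interventions:** keep this adjustment out of the primary model and label it supplementary, because it uses post-randomisation data.

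The cost is SAP wording: no new data, visits or patients.

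### The covariance structure of the primary NDI model is left to an unspecified data-driven choice, although an unstructured matrix could simply be pre-specified

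*Combined protocol and SAP*

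**What the plan says.** Section 8.0, main analysis for Aim 1, specifies a "linear mixed effect model with an appropriate covariance structure" for total NDI. The mean model is fixed: "Fixed effects will include treatment, time (as categorical), and treatment by time interaction". The time point is fixed too: "We plan intent-to-treat with the primary endpoint at 3 months". The covariance is not fixed. After looking at the within-subject associations, the team will "use a data driven approach in determining the appropriate variance-covariance structure". A reference marker follows that sentence. The same paragraph promises checks of assumptions and of model fit in all analyses.

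The text gives no list of candidate structures, no selection criterion, no fallback, no degrees-of-freedom method and no robust standard error. It does not say who makes the choice, when, or whether on data pooled over arms. Section 4.0 says that one person, whose name is removed, stays blinded to allocation, but does not tie this to the choice of covariance.

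On visits, the plan states "All outcomes will be collected at baseline, 1, 3, and 6 months", with the limit that "Six-month outcomes will only be collected for those who consent prior to approval of A033". The Aim 2 text sends the continuous secondary outcomes through the same approach, so the open choice recurs there.

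**The concern.** The trial is sized on the between-arm difference in NDI change from baseline to month 3. With categorical time, the model standard error of that contrast follows directly from the fitted baseline and 3-month variances and their correlation. A restrictive structure ties those quantities to the other visits. Compound symmetry uses one common variance and correlation. AR(1) by visit number makes the baseline-to-3-month correlation the square of the adjacent one. If the restriction is wrong, the standard error is too small or too large.

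With the rule unstated, an analyst could fit several structures, all defensible under the text, and obtain different primary p-values. A reader could not tell afterwards whether the reported one was chosen independently of the result. Selection would be worth that exposure if an unstructured matrix were hard to fit. With this number of visits and patients, it is not.

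**Working it through.** **1. The plan's own figures.** The target is "80% power to detect a 0.4 SD difference in change in NDI from baseline between TT-M and control with Type I error = 0.05". The normal approximation gives n = 2(1.960 + 0.842)²/0.4² = 98.1, so 99 per arm. The noncentral t gives 100 per arm, with power 80.4%. Then 200/0.76 = 263.2, so 264; 264 + 2×16 = 296; 16/0.76 = 21.05, so 22, and 264 + 2×22 = 308. All of the plan's figures are reproduced (two-sided test).

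**2. Is an unstructured matrix feasible?** Four visits need 4×5/2 = 10 covariance parameters; three visits need 3×4/2 = 6. These face 296 participants. In an assumed layout with 24% attrition and the 16 paused massage-arm patients, 112 + 101 = 213 have a 3-month value. About one third of patients were assumed to have no 6-month visit by design. The unstructured fit returned a finite solution in 184 of 184 simulated trials.

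**3. Large-sample effect of the structure.** Three patterns were assumed:
- (a) compound symmetry true, correlation 0.5;
- (b) standard deviations 0.8/1/1.1/1.1 with decaying correlation;
- (c) equal standard deviations with decaying correlation.

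Let k be the model standard error divided by the true standard error of the same estimator. Two-sided type I error is then 2Φ(−1.96k).

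| Pattern | Structure | k | Type I error | Model SE (SDs of change) | Power at 0.4 SD |
|---|---|---|---|---|---|
| a | Compound symmetry | 1.000 | 5.0% | 0.1313 | 86% |
| a | AR(1) | 1.183 | about 2% | 0.1571 | 76% |
| a | Unstructured | 1.000 | 5.0% | 0.1313 | 86% |
| b | Compound symmetry | 0.899 | 7.8% | 0.1198 | 89% |
| b | AR(1) | 1.033 | 4.3% | 0.1375 | 84% |
| b | Unstructured | 1.000 | 5.0% | 0.1323 | 86% |
| c | Compound symmetry | 0.896 | 7.9% | 0.1167 | 91% |
| c | AR(1) | 1.009 | 4.8% | 0.1305 | 87% |
| c | Unstructured | 1.000 | 5.0% | 0.1294 | 87% |

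As a plausibility check, a complete-case comparison of 112 with 101 has standard error √(1/112 + 1/101) = 0.137. The unstructured model is slightly below that because it also uses partial records.

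**4. What this does to a borderline p-value.** Take pattern (b), an unstructured result of exactly p = 0.05 (z = 1.96), and the same point estimate under each structure (an approximation). Compound symmetry gives z = 1.96 × 0.1323/0.1198 = 2.16, p = 0.030. AR(1) gives z = 1.96 × 0.1323/0.1375 = 1.89, p = 0.059. In small simulations at a true effect of 0.25 SD, the three structures disagreed on p < 0.05 in 14% of 100 trials under (a) and 8% of 84 trials under (b). Compound symmetry and unstructured alone disagreed in 3% and 6%. With so few trials these rates are rough.

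**5. Selection rules under the null.** A REML simulation used 10% loss by month 1, 24% by month 3, four assumed patterns and 1,000 runs each. The Monte Carlo standard error is √(0.05×0.95/1000) = 0.7 points.

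| Rule | Type I error over the patterns |
|---|---|
| Unstructured | 5.4-5.9% |
| Compound symmetry, imposed | 5.3-8.5% |
| AR(1), imposed | 2.1-5.5% |
| AIC or BIC pick | 4.8-6.8% |
| Smallest p-value | 5.9-8.8% |

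Under mild decay, BIC chose compound symmetry in 97% of runs, with a standard error 3.5% too small. That shortfall alone implies 2Φ(−1.96×0.965) = 5.9%, so part of the upper figure for AIC or BIC may be simulation noise. A separate simulation (148 per arm, three patterns, about 700 runs each) gave 6.8-7.9% for compound symmetry, 5.2-5.4% for unstructured and 4.8-5.3% for AIC or BIC.

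**The case against.** The strongest reply is that data-driven selection is not in itself harmful. A formal AIC or BIC pick kept type I error mostly near 5%, and in the smaller simulation could not be told apart from unstructured (Monte Carlo standard error about 0.8 points). This stands. The weakness is the unstated rule, and a named criterion would remove most of the harm.

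A reader might infer that the structure will be picked from unblinded data. The documents do not support this: within-subject associations can be examined pooled over arms, and the text is silent on timing and blinding. What can be said is that nothing requires the choice to precede unblinding.

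A reader might also take the figure of about 8% for compound symmetry as the plan's error rate. It is not. It comes from imposing that structure whatever the data show, under patterns where it is wrong. Where it is true, the rate is 5.0%. The promised check of model fit should catch a gross misfit, although it sets no threshold and would not settle a choice between structures that fit about equally well. AR(1), which the plan never proposes, mostly erred towards caution.

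Finally, the cited reference may hold the criterion. Even so, a reference marker alone does not tell the reader which rule binds the analyst.

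**Conclusion.** The point holds in a limited form. The plan fixes the outcome, fixed effects and primary time point, but leaves the covariance structure, and with it the standard error of the primary contrast, to a choice with no stated candidates, criterion or timing. If the choice were made freely for the smallest p-value, type I error could reach about 8-9%. Under a formal criterion it would be mostly near 5%, about 7% at worst in the patterns tried. The shift in any one trial is usually modest and decides the conclusion only near p = 0.05.

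All sizes rest on assumed NDI covariance patterns, attrition of 24% and an assumed share without a 6-month visit. The sample size is not affected. This is a nearly free improvement that should be made; it does not show that the planned analysis is invalid.

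**What to change.** In Section 8.0, replace the data-driven selection with text such as: *NDI and the repeated continuous secondary outcomes will be analysed with an unstructured covariance matrix and Kenward-Roger degrees of freedom. If that model does not converge, compound symmetry with a robust (sandwich) standard error will be used. Both are fixed before unblinding.* Another single simpler structure could serve as the fallback, provided it is named in advance.

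If the team prefers to keep selection, the minimum is to list the candidates, name the criterion and apply it to data pooled over arms before database lock. That closes most of the gap, but showed no advantage over unstructured in the patterns tried.

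The cost is two or three sentences. No extra patients or data are needed: with 296 enrolled, power at 0.4 SD under the unstructured model was 86-87% in the assumed patterns.

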To increase recruitment pool, an email blast will be sent out to an official VA mass email list that the recipients have consented to being on. This email group is specifically targeted towards veterans enrolled in healthcare in Indiana. The address is a no-reply address and veterans will be given only phone numbers for staff to protect their privacy.

To further increase recruitment, a single-slide informative visual will be placed on televisions in the Roudebush VAMC. This visual will include a graphic, a brief description of who would be eligible, a brief description of the commitment the study entails for the veteran, a brief description of the protocol, and contact information for the study team.

In addition to these measures, the study team will place lockboxes in the primary care clinics with a small advertisement for the study, using the same slide from the television ad.

The interested participants will be able to fill out an NDI at and place it in the lockbox. Study staff will collect these at the end of the day.

Randomization

Stratified and blocked randomization will be performed. After providing written-informed consent and completing their baseline interview, participants will be randomized to one of 2 arms:

- 1) Therapist-treated massage (TT-M)
- 2) Waitlist control (WL-C)

The randomization process will be directed by [name] (statistician) using statistical software with a random-number generator to create a list of group assignments before study recruitment begins. Randomization will be stratified by sex (men vs. women). Within strata, randomization with block sizes of 4 will be executed to ensure balance. Once an eligible participant has been screened, has signed informed consent, and has completed the baseline measures, the research assistant or project coordinator will pull the next sealed envelope. The randomization program locates the first unassigned record in the randomization list and assigns the participant to the group designated in that record. The participant identifier and date are written to the record. [name] will remain blinded to group assignment.

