8.0 Statistical Considerations

Sample size and power

The TOMCATT RCT was 'paused' on enrollment, study assessments, and massages in the TTM arm (massage arm) during an almost one year time period due to underlying safety concerns of trying to provide the intervention during the COVID-19 pandemic, although the control group was only 'paused' on enrollment. This impacted 16 patients enrolled in the TTM arm, of which 8/16 had completed their 1 Month assessment. The study will now be 'unpaused' for all, in which case new patients will be randomized and enrolled to the two study arms.

The primary intention-to-treat analysis will include all participants randomized and all assessments collected prior to pause for the TTM and all assessments for the waitlist control arm. Data will be analyzed as in the original analysis plan assuming data collection points were collected at TRT END and FOLLOW-UP on same time schedule (baseline, 1M, 3M, and 6M). Since 16 subjects were paused on their treatments and it has been over a year since they received a massage, for the primary analysis these patients will be considered lost-to-follow-up. Thus, we will recruit additional subjects to account for the increased LTF rate over what was originally expected due to COVID-19.

Original modification sample size: The modified study will focus on comparison of the TT-M and the waitlist control group (WL-C). We need 100 patients per group ($N = 200$) by 3 months to have 80% power to detect a 0.4 SD difference in change in NDI from baseline between TT-M and control with Type I error = 0.05 for the comparison of interest: TT-M vs WL-C. All analysis will be conducted under the intention-to-treat principle. Sample size was derived based on an independent two-sample t-test which is conservative compared to the contrast from our proposed linear mixed model.

Assuming total attrition for the TTM and WL-C arm is $(27+20)/(98+99) = 47/197 = 24\%$, we will seek to enroll a Total $N = 264$ ($200/.76$) or 132 per group in the TT-M and WL-C study groups. As we already have approximately 100 per group, with our current recruitment rate of 12 per month, we should be able to enroll an additional 64 subjects over 6 months.

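### Does the undefined Šídák adjustment in the primary NDI analysis take the 3-month contrast below its stated 80% power?

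*Combined protocol and SAP*

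**What the plan says.** Section 4.0 (Randomization) states that "participants will be randomized to one of 2 arms": therapist-treated massage (TT-M) and waitlist control (WL-C).

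Section 8.0 (New modification sample size) asks for 100 completers per group, which is to give "80% power to detect a 0.4 SD difference in change in NDI from baseline between TT-M and control with Type I error = 0.05". The basis is a two-sample t-test, which the plan calls conservative relative to its mixed model. Total enrolment is 296, with a ceiling of 308.

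Section 8.0 (Main analysis, Aim 1) fits a linear mixed model with treatment, categorical time and their interaction, to "compare the treatment arm to the control arm on rate of change as well as difference in outcome at the 3-month time point". It adds that "Difference in amount of change in outcome between groups at the other time points" (1 and 6 months) will also be estimated and reported. It then says that the Šídák "method to adjust for multiple comparisons. All analyses will include checking of assumptions and model fit", and closes with "We plan intent-to-treat with the primary endpoint at 3 months". The comparisons to be adjusted are neither listed nor counted.

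**The concern.** The Šídák threshold depends on the number of comparisons, so the rule cannot be applied until the family is known. With two arms there is one between-arm contrast at each time point, and hence nothing to adjust across arms. Read literally, what remains in the paragraph is the set of time points and the comparison of rates of change. Nothing expressly exempts the 3-month contrast.

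If that contrast is inside such a family, it is tested at a smaller alpha than the sample size assumed. A 3-month p-value between the Šídák threshold (0.0253 for two comparisons, 0.0170 for three) and 0.05 would then be positive on one reading and negative on the other. Leaving that choice until the results are known would be undesirable for a primary endpoint.

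**Working it through.** **Inputs.** From section 8.0: difference 0.4 SD, alpha 0.05, 100 completers per group, attrition 24%, enrolment 296 or at most 308, and 16 paused TT-M patients. The plan does not state sidedness; two-sided is assumed because it reproduces the plan's figure (one-sided 0.05 would give about 88%). Family sizes of two (for example 1 and 3 months) and three (1, 3 and 6 months) are assumptions; the plan gives no number.

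**The plan's own figure.** Noncentrality = 0.4 / √(1/100 + 1/100) = 2.828 on 198 degrees of freedom. Two-sided power at alpha 0.05 from the noncentral t is 80.4%, and the smallest n per group giving 80% is 100. The stated sample size is reproduced with no multiplicity adjustment.

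**Šídák thresholds.** Alpha per test = 1 − 0.95^(1/k).
- k = 1: 0.0500
- k = 2: 1 − 0.95^(1/2) = 0.0253
- k = 3: 1 − 0.95^(1/3) = 0.0170

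**Expected completers.** The plan says of the paused patients that "for the primary analysis these patients will be considered lost-to-follow-up", and raises enrolment to "have an additional 16 in the TTM arm to account for the 16 that were paused due to COVID". Applying 24% attrition equally to everyone else (an assumption):
- N = 296: TT-M (148 − 16) × 0.76 = 100.3; WL-C 148 × 0.76 = 112.5
- N = 308: TT-M (154 − 16) × 0.76 = 104.9; WL-C 154 × 0.76 = 117.0

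**Power for the 3-month contrast, true difference 0.4 SD, t-test basis.**

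| Completers (TT-M / WL-C) | k = 1 | k = 2 | k = 3 |
|---|---|---|---|
| 100 / 100 | 80.4% | 71.7% | 66.3% |
| 100.3 / 112.5 (N = 296) | 82.6% | 74.5% | 69.3% |
| 104.9 / 117.0 (N = 308) | 84.2% | 76.5% | 71.5% |

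If 0.4 SD is the truth, the chance of a p-value in the disputed range is the difference between columns. At 100 per arm this is 80.4 − 71.7 = 8.7% (k = 2) or 80.4 − 66.3 = 14.1% (k = 3). At N = 296 it is 8.1% or 13.3%.

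**Which column applies?** The arithmetic cannot settle this; the text has to.

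1. Both sample-size paragraphs assign the full 0.05 to one comparison of interest, TT-M against WL-C, by 3 months. The Aim 1 paragraph names 3 months as the primary endpoint and gives the other time points a reporting role.
2. Section 5.0 (Remove Care-Ally Arm) records that a further massage arm was dropped. Multi-arm wording survives elsewhere: k-sample tests for baseline comparisons in section 8.0, and care-ally training among the intervention costs.
3. The responder analysis under Aim 2 repeats the Šídák sentence. There it follows directly on a statement that the main contrasts are those at 3 months between more than one treatment and control. It comes before the sentence on reporting other time points. In that position its family is arms against control at 3 months.
4. With the care-ally arm gone, that family has one member: k = 1, alpha 0.05, first column of the table.

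**Rate of change.** With categorical time there is no single slope, but the treatment-by-time interaction has a joint test, so the phrase does refer to a defined hypothesis. Nothing in the plan makes it a co-primary test.

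**The case for a change.** The strongest counter-argument is that the adjustment sentence sits in the primary-outcome paragraph, just before the primary endpoint is named, with no exemption. The phrase about several treatments that reveals the across-arm family under Aim 2 does not appear under Aim 1. An analyst could therefore apply Šídák across time points by default. The remark that the t-test is conservative is no firm rescue. To restore 80% at 100 per arm, the mixed model would have to cut the variance of the contrast by 17% (k = 2) or 24% (k = 3), and the plan gives no correlation from which to check this.

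Much of this stands. The family is unwritten, the leftover-wording explanation is an inference, and the power figures are right under their condition. What does not follow is that the plan's power is overstated. The condition requires setting aside the sample-size statement and the named primary endpoint in favour of a family that the document never describes. If an analyst did adjust across time points, the error would be in the conservative direction for the primary claim.

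**Conclusion.** No change to the plan follows. The missing family is a gap in definition, probably left by removal of the care-ally arm, and the rest of section 8.0 indicates how to fill it: the 3-month TT-M against WL-C contrast is the one primary test, at two-sided 0.05. On that reading power is 80.4% at 100 completers per arm and about 82.6% with the completers expected from 296 enrolled.

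The lower figures (74.5% for a family of two and 69.3% for three, at N = 296) would matter only if the sponsor meant the primary contrast to share its alpha with other time points, which nothing in the plan states. Type I error for that contrast is at most 0.05 either way, and neither sample size nor data collection is affected.

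The conclusion rests on reading the Šídák sentence as an across-arm adjustment, on a two-sided test, and, for the N = 296 figures, on 24% attrition in both arms once the 16 paused patients are set aside.
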